## 7. PLANNED ANALYSIS

Safety analysis (refer to [Section 7.8](#)) will be performed by the [REDACTED] and will be presented in Sections 9.1 to 9.4 of the CTR and in Appendix 10.6 and 10.5.1.

Statistical model-based analysis of PK and [REDACTED] will be performed by BDS and will be presented in Section 9.5 of the CTR and in Appendix 10.5.3.

Descriptive data analysis of PK and [REDACTED] will be performed by the [REDACTED] and will be presented in Section 9.6 and 9.7 of the CTR and in Appendix 10.5.5 and 10.5.6.

The format of the listings and tables will follow the BI standards ([7](#)) with the exception of those generated for PK-calculations following BI standards for PK/PD analysis ([8](#)).

The individual values of all subjects will be listed, sorted by study group, subject number, and visit. The listings will be included in Appendix 10.6 of the CTR.

For End-Of-Text tables, the set of summary statistics for continuous variables is:

N	number of non-missing observations
Mean	arithmetic mean
SD	standard deviation
Min	minimum
Median	median
Max	maximum

For analyte concentrations and PK parameters, the following descriptive statistics will additionally be calculated:

Nobs	number of observations
CV	arithmetic coefficient of variation
gMean	geometric mean
gCV	geometric coefficient of variation
P10	10th percentile
Q1	1st quartile
Q3	3rd quartile
P90	90th percentile

The data format for descriptive statistics of concentrations will be identical to the data format of the respective concentrations. The descriptive statistics of PK parameters will be calculated using the individual values with the number of decimal places as provided by the evaluation

program. Then the individual values as well as the descriptive statistics will be reported with three significant digits in the CTR. The estimated values of inferential statistics analysis will be rounded to 2 decimal places.

Descriptive statistics of PK parameters and [REDACTED] will be calculated if  $N \geq 2$  in each study group.

Data of a study group will be included in the regression model if  $N \geq 3$  subjects contribute with data.

It should be noted that due to the exploratory nature of the analyses and due to the possibly relatively small number of subjects in a study group, the descriptive statistics or statistical results should be interpreted generally with caution. (When the number of subjects is low, data of single subjects has a higher impact on results.)

Tabulations of frequencies for categorical data will include all possible categories and will display the number of observations in a category as well as the percentage (%) relative to the respective study group (unless otherwise specified, all subjects in the respective subject set whether they have non-missing values or not).

The precision for percentages should be one decimal point, unless the denominator is smaller than 100 (in all treatment columns), in which case percentages are given in integer numbers. The category missing will be displayed only if there are actually missing values.

Units of variables should be given in the titles or column/row descriptors in brackets (e.g. (mg)).

## **7.1 DEMOGRAPHIC AND OTHER BASELINE CHARACTERISTICS**

Only descriptive statistics are planned for this section of the report, based on the TS. The data will be summarised by study group and additionally in total for the Appendix 10.5.1.4:1.

## **7.2 CONCOMITANT DISEASES AND MEDICATION**

Concomitant diseases will be coded using the latest version of the coding system of the Medical Dictionary for Drug Regulatory Activities (MedDRA). Concomitant medications will be coded using the latest version of the World Health Organization Drug Dictionary (WHO-DD). The coding version number will be displayed as a footnote in the respective output.

Only descriptive statistics are planned for this section of the report, based on the TS. The data will be summarised by study group.

The relevance of the concomitant therapies to the evaluation of PK will be decided no later than at the final RPM.

## **7.3 TREATMENT COMPLIANCE**

### **Section 4.5 of the CTP:**

*Compliance will be assured by administration of trial medication in the study centre under supervision of the investigating physician or a designee by the so-called four-eye principle (two-person rule). For this, one authorised employee of the trial site should witness the administration of trial medication, and – if applicable – its preparation (e.g., reconstitution), if correct dosage cannot be ensured otherwise. The measured plasma concentrations and urinary excretion of trial medication will provide additional confirmation of compliance.*

Treatment compliance will not be analysed as a specific endpoint. Any deviation from complete intake will be addressed in the final RPM (see [Section 6.2](#)) and described in the CTR.

## 7.4 PRIMARY OBJECTIVE ANALYSIS

Independent of the main objectives stated in the CTP, this section describes further details of the primary endpoint analyses outlined in the CTP.

### 7.4.1 Main analysis

*The primary endpoints as specified in section 2.2 will be calculated according to the BI Standard Operating Procedure (SOP) 'Standards and processes for analyses performed within Clinical Pharmacokinetics/Pharmacodynamics' (001-MCS-36-472[sic]). The analysis will be based on the PKS and will be descriptive in nature.*

*The statistical model used for the analysis of the primary endpoints will be an analysis of variance (ANOVA) model on the logarithmic scale. That is, the PK endpoints will be log-transformed (natural logarithm) prior to fitting the ANOVA model. This model will include effects accounting for the following sources of variation: '[study] group', age, and BMI. All effects will be considered as fixed. The model is described by the following equation:*

$$y_{km} = \mu + \pi_k + age_m + BMI_m + e_{km},$$

where

- $y_{km}$  = logarithm of response measured on subject  $m$  [from study group]  $k$ ,
- $\mu$  = the overall mean,
- $\pi_k$  = the  $k$ th [study] group effect, i.e. degree of hepatic impairment,  $k=1$  for healthy/normal (Group 1), 2 for Group 2 [Child-Pugh A] or 3 for Group 3 [Child-Pugh B] respectively,
- $age_m$  = the age of subject  $m$ ,
- $BMI_m$  = the BMI of the subject  $m$ ,
- $e_{km}$  = the random error associated with the  $k$ th [study] group effect for subject  $m$
- where  $e_{km} \sim N(0, \sigma_k^2)$  i.i.d,

*Point estimates for the ratios of the geometric means (test [T]/reference [R]) for the primary endpoints (see section 2.2) and their two-sided 90 % confidence intervals (CIs) will be provided [where reference is healthy subjects and the test group are the individual patient groups].*

[figure not shown]
*For each endpoint, the difference between the expected means for  $\log(T)-\log(R)$  will be estimated by the difference in the corresponding adjusted means (Least Squares Means).*

*Additionally, their two-sided 90% confidence intervals will be calculated based on the residual error from the ANOVA and quantiles from the t-distribution. These quantities will then be back-transformed to the original scale to provide the point estimate and 90 % CIs for each endpoint.*

Note: 001-MCS-36-472 = BI-KMED-TMCP-HTG-0025 & BI-KMED-TMCP-MAN-0014 ([4](#), [5](#); BI SOP was replaced).

All parameters are calculated and analysed descriptively by study group in addition to the model-based approach.

These analyses will be based on the PKS.

[figure not shown]

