3. DESCRIPTION OF DESIGN AND TRIAL POPULATION

3.1 OVERALL TRIAL DESIGN

Study Design

This study will primarily investigate, following a single dose of the cocktail, the pharmacokinetic profiles for each of the cocktail components (digoxin, furosemide, metformin and rosuvastatin) up to [REDACTED] postdose, calculating the resulting C_{max} and $AUC_{0-[\text{REDACTED}]}$ values. Urinary excretion will also be investigated as a further endpoint. The cocktail will be given after a standardized breakfast.

Note: The cocktail should only be given to subjects/patients who are not already on any of the cocktail components. Otherwise, the resulting drug concentrations of that moiety will not be meaningful in the current study.

An exploratory analysis of endogenous biomarkers CP I, CP III NMN, and m1A will be undertaken, if the data allows.

[REDACTED]

The current study consists of 3 groups:

- **Healthy subjects**
Group 1: 12 healthy subjects (matched as far as possible (see section [3.2](#)) to the patients in group 2)
- **Liver cirrhosis patients**
Group 2: 12 F4 Child-Turcotte-Pugh class A (Child-Pugh A) subjects (compensated)
Group 3: 06 F4 Child-Turcotte-Pugh class B (Child-Pugh B) subjects (decompensated)

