3.2 DISCUSSION OF TRIAL DESIGN, INCLUDING THE CHOICE OF CONTROL GROUP(S)

For this trial, as there is only one treatment, an open label study is preferred. The open-label treatment is not expected to bias results, since the primary study endpoints are quantitative endpoints derived from measurement of plasma concentrations of the analytes. The control group are healthy volunteers, where feasible, will be matched in terms of age (± 10 years), BMI (± 20 %) and sex. This may result in the liver cirrhosis patients as a group being different from the healthy subjects, if the number of liver cirrhosis patients are outside the BMI range for healthy subjects. However, all comparisons will be conducted on a group basis, not on individual matched subjects.

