3.3.2 Inclusion criteria

Healthy subjects and patients will only be included in the trial if they meet the following criteria:

Healthy subjects and F4 liver cirrhosis patients

1. Signed and dated written informed consent in accordance with the International Conference on Harmonisation-Good Clinical Practice (ICH-GCP) and local legislation prior to admission to the trial
2. Either male subject, or female subject who meets any of the following criteria for a highly effective contraception from at least 30 days before the first administration of trial medication until 30 days after trial completion:
 - Use of combined (estrogen and progestogen containing) hormonal contraception that prevents ovulation (oral, intravaginal, or transdermal), *plus condom*
 - Use of progestogen-only hormonal contraception that inhibits ovulation (only injectables or implants), *plus condom*
 - Use of intrauterine device (IUD) or intrauterine hormone-releasing system (IUS)
 - Sexually abstinent
 - A vasectomised sexual partner who received medical assessment of the surgical success (documented absence of sperm) and provided that the partner is the sole sexual partner of the trial participant
 - Surgically sterilised (including hysterectomy)
 - Postmenopausal, defined as no menses for 1 year without an alternative medical cause (in questionable cases a blood sample with levels of FSH above 40 U/L and estradiol below 30 ng/L is confirmatory)
3. Not taking any components in the cocktail within 4 weeks of enrolment

Healthy subjects only

4. Healthy male or female subjects according to the assessment of the investigator, as based on a complete medical history including a physical examination, vital signs (BP, PR), 12-lead ECG, and clinical laboratory tests
5. Age of 18 to 75 years (inclusive)
6. BMI of 18.5 to 35 kg/m² (inclusive). A BMI of \geq 30 is no exclusion criterion when the subject can be considered healthy apart from the elevated BMI
7. Subjects to be matched for age (\pm 10 years), BMI (\pm 20 %) and sex to subjects in Group 2
8. Have no known or suspected hepatic impairment and meet the following criteria at the screening visit: alanine aminotransferase (ALT) \leq ULN, aspartate aminotransferase (AST) \leq ULN, total bilirubin \leq ULN, albumin \leq ULN, prothrombin time \leq ULN

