5.2.5 Medical examination

The medical examination will include:

- Demographics (height in cm, body weight in kg, age on the day of informed consent (in years), sex (male, female to describe the subject's sex at birth), gender identity (male, female, and other to describe how the subject self identifies regardless of their genotypic or phenotypic sex)
- Smoking and alcohol history
- Assessment of smoking and drinking habits at the timepoint of screening
- Relevant medical history (including trial indication and concomitant diseases, if applicable)
- Relevant concomitant therapy (including start date, if applicable)
- Review of inclusion and exclusion criteria (see section [3.3.2](#) and [3.3.3](#))
- For females: of childbearing potential yes/no to characterize the patient population and as a basis for contraception requirements

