7.1 NULL AND ALTERNATIVE HYPOTHESES

It is not planned to test any statistical hypotheses in a confirmatory sense.

The relative bioavailability of rosuvastatin, digoxin, metformin, and furosemide in compensated and decompensated F4 liver cirrhosis patients (Child-Pugh A and Child-Pugh B) compared with healthy subjects (reference) will be estimated by the ratios of the geometric means (test/reference) for all PK endpoints and their corresponding 2-sided 90 % confidence intervals (CIs) will be provided. This method corresponds to the two one-sided t-test procedure, each at the 5 % significance level. Since the focus is on estimation and not testing, a formal hypothesis test and associated acceptance range is not specified.

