7.2.2 Primary objective analyses

Primary analyses

The primary endpoints as specified in section [2.2](#) will be calculated according to the BI Standard Operating Procedure(SOP) 'Standards and processes for analyses performed within Clinical Pharmacokinetics/Pharmacodynamics' ([001-MCS-36-472](#)). The analysis will be based on the PKS and will be descriptive in nature.

The statistical model used for the analysis of the primary endpoints will be an analysis of variance (ANOVA) model on the logarithmic scale. That is, the PK endpoints will be log-transformed (natural logarithm) prior to fitting the ANOVA model. This model will include effects accounting for the following sources of variation: 'group', age, and BMI. All effects will be considered as fixed. The model is described by the following equation:

$$y_{km} = \mu + \pi_k + \text{age}_m + \text{BMI}_m + e_{km}, \text{ where}$$

- y_{km} = logarithm of response measured on subject m receiving treatment k,
- μ = the overall mean,
- π_k = the kth group effect, i.e. degree of hepatic impairment, k = 1 for healthy/normal (Group 1), 2 for Group 2 or 3 for Group 3 respectively,
- age_m = the age of the subject m,
- BMI_m = the BMI of the subject m,
- e_{km} = the random error associated with the kth group effect for subject m
- where $e_{km} \sim N(0, \sigma_k^2)$ i.i.d,

Point estimates for the ratios of the geometric means (test/reference) for the primary endpoints (see section [2.2](#)) and their two-sided 90 % confidence intervals (CIs) will be provided.

For each endpoint, the difference between the expected means for log(T)-log(R) will be estimated by the difference in the corresponding adjusted means (Least Squares Means). Additionally, their two-sided 90% confidence intervals will be calculated based on the residual error from the ANOVA and quantiles from the t-distribution. These quantities will then be backtransformed to the original scale to provide the point estimate and 90 % CIs for each endpoint.

Further exploratory analyses

In addition to the model-based approach all parameters will be calculated and analysed descriptively.

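### Sex is one of three matching factors but the only one left out of the primary model, so the Child-Pugh B/healthy ratio is neither matched nor adjusted for sex

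*SAP*

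**What the plan says.** Protocol 3.2 says that the healthy controls, "where feasible, will be matched in terms of age (± 10 years), BMI (± 20 %) and sex". Inclusion criterion 7 in Protocol 3.3.2 ties this to one patient group, requiring a match for age, BMI "and sex to subjects in Group 2". Protocol 3.1 also refers to Group 2 and softens the rule to "matched as far as possible". Group 2 is Child-Pugh A. No section matches controls to Group 3 (Child-Pugh B) or sets a sex quota for it.

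Protocol 3.2 adds that "all comparisons will be conducted on a group basis, not on individual matched subjects".

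The primary model is the same in both documents. Protocol 7.2.2: "This model will include effects accounting for the following sources of variation: 'group', age, and BMI". SAP 7.4.1: "This model will include effects accounting for the following sources of variation: '[study] group', age, and BMI". The equation in each has no sex term, and SAP section 4 lists no covariate change. SAP 7.4.1 compares each patient group separately with healthy subjects, so Child-Pugh B/healthy is a primary contrast.

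Protocol 7.2.2.1 to 7.2.2.3 plan no sensitivity, subgroup or supplementary analysis. Sex is recorded under Protocol 5.2.5 as "sex (male, female to describe the subject's sex at birth". SAP 7.1 summarises demographics descriptively by study group.

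**The concern.** By matching on sex, the sponsor treats it as a possible confounder. For age and BMI, the model makes up for the missing match to Group 3. For sex, nothing does. The Child-Pugh A/healthy ratio is partly protected, since its matching is qualified and no matched-pair structure enters the analysis.

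The trial is non-randomised, and its product is a set of ratios with 90% intervals. Protocol 7.1 gives the reason for having no formal test: "Since the focus is on estimation and not testing". Confounding bears directly on such an estimate. If sex affects exposure at a given age and BMI, a different sex mix in Group 3 would be read as an effect of hepatic impairment, in the comparison with the fewest patients. A demographic table would reveal the imbalance but would not correct the ratio.

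**Working it through.** The plan states no power, SD, effect size or sex effect, so it has no figure of its own to reproduce. The check compares design with model and then sizes the gap.

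**Factors side by side**

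| Factor | Matched to Group 2 | Matched to Group 3 | In primary model |
|---|---|---|---|
| Age | where feasible, ±10 years | no | yes |
| BMI | where feasible, ±20% | no | yes |
| Sex | where feasible | no | no |

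**Inputs.** Group sizes are 12, 12 and 6 (Protocol 7.5, SAP 6.1), with two-sided 90% intervals (Protocol 7.1). The following are assumptions: a sex ratio in exposure of 1.2 to 1.4, a residual log-SD of 0.3 to 0.5, one common residual variance, and age and BMI unrelated to sex and group.

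**Shift in the ratio** = (sex ratio)^(difference in female share):

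| Difference | Sex ratio 1.2 | Sex ratio 1.4 |
|---|---|---|
| 25 points | 1.2^0.25 = 1.05 | 1.4^0.25 = 1.09 |
| 33 points | 1.2^(1/3) = 1.06 | 1.4^(1/3) = 1.12 |
| 50 points | 1.2^0.5 = 1.10 | 1.4^0.5 = 1.18 |

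The shift is smaller if BMI absorbs part of the sex effect.

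**Chance of imbalance** (exact binomial, both groups from one sex mix, 50%, 60% or 70% one sex):

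| Gap at least | 12 vs 6 | 12 vs 12, no matching |
|---|---|---|
| 25 points | 0.41 / 0.40 / 0.37 | 0.31 / 0.30 / 0.26 |
| 33 points | 0.25 / 0.24 / 0.20 | – |
| 50 points | 0.065 / 0.059 / 0.043 | – |

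The last column is an upper bound for Child-Pugh A, since any matching lowers it. A systematic sex difference between Group 3 and the controls would raise the 12 vs 6 figures.

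**Coverage of the unadjusted 90% interval, given the split.** Groups 1 and 2 are set at 6/12 female. The bias is ln(sex ratio) × difference in share. The SE is SD × √(1/12 + 1/6) = SD × 0.5. The residual sum of squares over SD² is noncentral chi-square on 25 df, because the omitted sex effect inflates it. From 400,000 draws per setting, over the assumed ranges:

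- Group 3 with 0/6 female: 78% to 88%
- 1/6 female: 87% to 90%
- 2/6 female: about 90% to 93%

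**Cost of adding sex.** Residual df go from 30 − 5 = 25 to 30 − 6 = 24, and the t quantile from 1.708 to 1.711. The variance factor of Group 3 minus Group 1, from the inverse of X′X, changes as follows at fixed residual SD:

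| Group 3 female | Without sex | With sex | Rise in SE |
|---|---|---|---|
| 0/6 | 0.2500 | 0.2917 | 8.0% |
| 1/6 | 0.2500 | 0.2663 | 3.2% |
| 2/6 | 0.2500 | 0.2538 | 0.8% |

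The net effect on the interval can go either way, because the sex term also removes variance from the residual. At log-SD 0.4 the interval's fold factor goes from 1.42 to 1.45 (0/6 female, sex ratio 1.2) or from 1.46 to 1.41 (2/6 female, sex ratio 1.4).

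**The case against.** The strongest counter-argument is that chance imbalance is not bias. If Group 3 and the controls come from the same sex mix, the unadjusted ratio is right on average and the unmodelled sex variation sits in the residual error. Simulated over such a common mix, the current model's 90% interval for Child-Pugh B/healthy covers 89% to 91%, against 90% to 91% with sex added. That is correct: the low coverage above is conditional on a particular split. But nothing in a non-randomised design ensures a common sex mix between Child-Pugh B patients and controls chosen to resemble Child-Pugh A patients. And once a split has been observed, the conditional figure is the one that bears on the reported ratio.

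Other points stand in part:

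- The worst case is rare by chance. An all-one-sex Group 3 from a 50:50 mix has probability 2 × 0.5^6 = 0.031, and there the adjustment is weakest.
- Every effect size is assumed, and even 1.18 is far from 2-fold.
- Age and BMI are matched within tolerances, so they need a model term even after successful matching, whereas a sex match is exact when achieved. This is a fair reading for Group 2 but gives Group 3 nothing.
- The trial is exploratory, and SAP section 7 advises caution with small groups. That limits the claims made but does not remove confounding.
- The SAP contents list has a redacted entry between 7.4.1 and 7.5, so a SAP sensitivity analysis including sex cannot be ruled out. The primary model itself is legible and has no sex term.

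**Conclusion.** The concern holds. Sex is the only matching factor missing from the primary model, and for Child-Pugh B/healthy neither design nor analysis controls it. Under an assumed 1.2- to 1.4-fold sex effect, the shift is 1.05 to 1.18 for imbalances of 25 to 50 points. This is modest beside the 2-fold threshold, although it could move a ratio or interval limit lying near it. Loss of coverage is material only at large imbalance. The matter is one of estimation bias, not type I error. The change should be made because it is cheap and follows the sponsor's own choice of matching factors; the omission would not by itself invalidate the trial.

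**What to change.** Add sex as a fixed effect to the primary model in Protocol 7.2.2 and SAP 7.4.1, giving study group, sex, age and BMI. Report the ratios from the current model without sex alongside, as a sensitivity analysis. State that if Group 3 turns out to be all one sex, its adjusted ratio relies on the sex effect estimated in Groups 1 and 2.

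No new data are needed. The price is the one degree of freedom and the loss of precision tabulated above, which is negligible when sex is balanced and grows with the imbalance, when adjustment is most needed. Fixing the term in advance also avoids an ad hoc choice of covariates once the sex split is known in this open-label trial.

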## **7.5 SECONDARY OBJECTIVE ANALYSIS**

[figure not shown]
### **7.5.1 Key secondary objective analysis**

This section is not applicable as no key secondary endpoint has been specified in the protocol.

### **7.5.2 Secondary objective analysis**

This section is not applicable as no secondary endpoint has been specified in the protocol.

### **7.6.3 Safety endpoints**

Safety endpoints and tolerability will be analysed as described in [Section 7.8](#) of this TSAP.

